TITLE	Assessing the Impact of eSight Go At-Home Usage in Individuals with Visual Impairment
SHORT TITLE	eSight
PROTOCOL NO.	00085670
SPONSOR	Gentex Corporation
INVESTIGATOR	[name]
ADDRESS	[name]
[contact]
EMAIL	[contact]
VERSION	7.0
DATE	04/18/2025

Contents

Brief Overview	3
Section 1: Procedures	3
1.1 Screening/Recruitment Procedures.....	3
1.1.1 Inclusion/Exclusion Criteria.....	3
1.2 Informed Consent Process	4
1.3 Assessments.....	4
1.4 Intervention	5
1.5 Data Analysis.....	5
Section 2: Risk Information	6
2.1 Risks, Side Effects, and/or Discomforts	6
2.2 Alternatives to Participation	6
2.3 Cost	6
Section 3: Monitoring/Reporting of AE/SAE	6
Section 4: Study Oversight	7
Section 5: Data Management	7

Brief Overview

The purpose of the study is to assess the effect of the updated version of Gentex's device, eSight Go, an image-enhancing wearable device to assist those with vision impairment. The study will comprise at least 50 vision impaired individuals to evaluate the efficacy or improvements in visual, quality of life, and mobility arising from the use of eSight Go. The primary aim of the study is to measure the effect of eSight Go on visual acuity, reading performance, and quality of life. The secondary aim is to measure the impact of eSight Go on mobility, balance, cybersickness, and user satisfaction. The study assessments will take place at the Brooks Rehabilitation Clinical Research Center at 4 time points:

- 1) at visit 1 before using the device;
- 2) during visit 1, while using the device;
- 3) at visit 2, while using the device; and,
- 4) during visit 2 without the device.

Participants will receive a personal eSight device and comprehensive training on its operation at visit 1. They will then use the unit in daily living, such as home, work, or school settings, over a period of 4 weeks, and then return for visit 2. If prescription lenses are determined to be needed to correct refractive error, visit 1 will be divided into 2 visits to allow time for the lenses to be ordered prior to starting the at-home trial period.

Section 1: Procedures

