1.1.1 Inclusion/Exclusion Criteria

Inclusion Criteria

- Aged 18 to 90.
- Best-corrected visual acuity between 20/50 to 20/400 in the better eye.
- Subjects who have been diagnosed with an ocular condition causing visual impairment
- Have a functional binocular field of view of at least 20 degrees.
- Visual status stable for at least six months.
- Demonstrate visual benefit from magnification.
- Agree to wear the eSight Go in a variety of situations in the home and community.
- Score ≥ 20 on the Short Orientation-Memory-Concentration Test of Cognitive Impairment (OMCT).
- Subject must be able to provide an informed consent
- Subject must agree to use eSight Eyewear only under conditions that will not jeopardize the safety of either the user or the device.

Exclusion Criteria

- Participant must not be currently undergoing any medical or surgical procedures resulting in unstable vision.

- Participants who have undergone cataract, refractive, or other surgical procedures related to vision in the six-month period prior to study enrollment.
- Severe (>20/400) visual impairment in the better seeing eye.
- Cognitive limitations (< 20 on OMCT).
- Participants who have undergone any vision-related injections (e.g. anti-VEGF) in the two-month period prior to the study because of active bleeding in the retina. Ongoing anti-VEGF treatments are permitted if the participant is in a "Treat and Extend" or pro re nata ("PRN") disease management, and macula is dry.
- Participants are unable or unwilling to adhere to the examination schedules as they are described in the study protocol. This may also include participants already enrolled, who for whatever reason, have become unable or unwilling to continue the study. This may also include participants for whom the travel time to/from the study site is unacceptable.
- Participants who self-report a history of alcoholism, drug abuse, or psychosis.
- Participants who exhibit clinical evidence of depression, poor motivation, emotional or intellectual problems, or any other conditions which would likely limit validity of consent or appropriate responses to participate in the study or who are deemed unsuitable psychologically or physiologically for study participation by the investigator.
- Participants who may have a conflict of interest with eSight Corp, which could reasonably influence their participation in the study.

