- Refractive error outside the range correctable by lens inserts in the device (> +/-8.00 D sph or -4.00 cyl)

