1.3 Assessments

Participants will complete assessments four times, twice at visit 1 and twice at visit 2, except for the OMCT and the refraction which will only be performed once at visit 1.

Study Timeline

5/2025	5/2025-4/2026			5/2026-7/2026
Open enrollment	Visit 1	4 Weeks At Home Usage	Visit 2	Complete Analysis, Study Close Out

Assessments will include the following procedures:

Primary Aim Assessments (Visual)

- Early Treatment Diabetic Retinopathy Study Chart (ETDRS)
- MNREAD
- MARS Test
- NEI VFQ-25
- Reading Behavior Inventory
- Refraction Test

Secondary Aim Assessments (Mobility & Cognitive)

- Dynamic Gait Index
- Timed Up and Go
- Spatiotemporal Gait Kinematics
- OMCT
- PROMIS Short Form v2.0 - Cognitive Function 8a

Questionnaires

- Demographic information
- Ophthalmic History
- 36-Item Short Form Health Survey
- Cybersickness in Virtual Reality
- Device Usage Willingness and Participation
- Activities Balance Confidence Scale

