2.3 Cost

There is no monetary compensation for participation in this study. We will provide a travel reimbursement for enrolled participants of \$25 per visit, up to \$50 per participant. This will be paid to the participant in the form of a Visa gift card.

Section 3: Monitoring/Reporting of AE/SAE

Records of participation in this study will be held confidential except when sharing the information is required by law or as described in this informed consent. The Investigator, the sponsor or persons working on behalf of the sponsor, and under certain circumstances, the United States Food and Drug Administration (FDA) and the Institutional Review Board (IRB) will be able to inspect and copy confidential study-related records. This means that absolute confidentiality cannot be guaranteed. If the results of this study are published or presented at meetings, they will be de-identified.

Participant vitals and visual and physical comfort will be monitored by study staff throughout the assessments. Participants will self-report any visual or physical discomfort during the weekly check ins with a study team member. Any abnormal or adverse responses to utilizing the device will be reported to the study physician who will provide medical recommendations for proceeding or terminating use of the device. Repeated and unresolved abnormal responses will result in withdrawal from the study under the advisement of the study physician. All adverse events will be tracked and reported to the IRB, primary investigator, and study physician.

Section 4: Study Oversight

[name], who has been practicing for 12 years and participating in research for 10 years, will serve as the principal investigator and maintain administrative oversight of this study, ensuring compliance with this protocol, related policies and procedures of Brooks Rehabilitation, and relevant rules and regulations.

Collection, recording, and reporting of data will be accurate and will ensure the privacy, health and welfare of participants. All study documents and procedures will be made available for monitoring, auditing, IRB review and regulatory inspection as required by the IRB and/or by law. The study will be discontinued if the principal investigator, the Brooks Center for Low Vision, or the IRB determines necessary. The principal investigator will promptly inform the IRB and provide the reason(s) for the termination or suspension of the study.

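### Does splitting visit 1 for lens fitting break the visit schedule, the travel payment or the visit 1 on-device test?

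*Protocol*

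**What the plan says.** The Brief Overview sets four time points: without the device and then with it at visit 1, and with the device and then without it at visit 2. The second is described as "during visit 1, while using the device". For anyone whose refraction shows a need for lenses, it adds that "visit 1 will be divided into 2 visits to allow time for the lenses to be ordered prior to starting the at-home trial period".

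Section 1.3 keeps to the two named visits: "Participants will complete assessments four times, twice at visit 1 and twice at visit 2". The refraction is done once, at visit 1. Section 1.1.1 shows that the correction sits in the device, since it excludes "Refractive error outside the range correctable by lens inserts in the device". It also excludes people who are "unable or unwilling to adhere to the examination schedules as they are described in the study protocol", and mentions "participants for whom the travel time to/from the study site is unacceptable".

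Section 2.3 reimburses travel at $25 for each visit, with a ceiling of $"50 per participant. This will be paid to the participant in the form of a Visa gift card".

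Section 1.5 describes the analysis as a pre- to post-testing comparison and does not say which of the four time points form the pair.

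**The concern.** Three things look out of step.

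- **Payment.** A participant with a split visit 1 travels three times, but the cap equals two visits at the stated rate. The extra trip falls on those who need lenses, in a protocol that names travel time as a reason for exclusion.
- **Schedule.** Neither the list of time points nor Section 1.3 says which part of a split visit 1 holds the off-device set, the on-device set, or the hand-over and training. People can nevertheless be excluded for not keeping to the described schedule.
- **Lens timing.** The only deadline given for the lenses is the start of home use. If the visit 1 on-device set were done before the inserts arrived, these participants would be tested on the device uncorrected at visit 1 and corrected at visit 2. The on-device change between visits would then mix new lenses with four weeks of home use, and the immediate device effect at visit 1 could be understated. This would touch the ETDRS, MNREAD and MARS tests, all listed under the primary aim.

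The third point is the only one that could reach a result.

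**Working it through.** **Payment.** Inputs from Section 2.3: $25 per visit and a cap of $50. From the Brief Overview: one extra attendance when visit 1 is split, and at least 50 participants.

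- The plan's own figure: 2 × $25 = $50, equal to the cap.
- Split visit 1, each part paid as a visit: 3 × $25 = $75.
- Difference: $75 − $50 = $25, which is 25/75 = 33% of the uncapped amount. The cap spread over three trips is 50/3 = $16.67 per trip.
- Study total for 50 participants: 50 × share × $25. The share needing lenses is not given, so it is an assumption: 0 gives $0, 0.2 gives $250, 0.6 gives $750 and 1.0 gives $1,250.

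The $75 arises only if each part counts as a separate paid visit. Even then Section 2.3 sets a ceiling, and a ceiling of $50 holds for any number of trips. If the two parts count together as visit 1, the payment is 2 × $25 = $50 and there is nothing to reconcile.

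**Schedule.** The Brief Overview divides visit 1; it does not add a visit with a new name. Two assessment sets at visit 1 and two at visit 2 therefore remains a true description whether visit 1 takes one day or two. The trigger for the split, the number of parts and the purpose are all stated, so the adherence criterion has a schedule to refer to. What is unwritten is which part holds which test.

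**Lens timing.** Label the time points 1 (visit 1, off), 2 (visit 1, on), 3 (visit 2, on) and 4 (visit 2, off). Four time points give six pairs:

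| Pair | Uses time point 2? |
|---|---|
| 1 vs 2 | yes |
| 2 vs 3 | yes |
| 2 vs 4 | yes |
| 1 vs 3 | no |
| 1 vs 4 | no |
| 3 vs 4 | no |

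Only the first three can carry the problem, and Section 1.5 does not name any of them as the planned comparison. For one of them to be affected, two further things must hold: the on-device set is run before the inserts arrive, and the missing correction changes the score. The protocol states neither. It equally allows both sets to be run in the second part, with inserts fitted, and then no mixing occurs.

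If instead the off-device set is done in the first part and the on-device set in the second, time points 1 and 2 fall on different days for this subgroup. Section 1.1.1 requires visual status to have been stable for at least six months, so a wait for lenses should matter little, although its length is not stated.

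No acuity bias is calculated, because the protocol gives no distribution of refractive error, no share needing lenses and no score per dioptre.

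**The case for a change.** The best case for a change is that the correction worn during testing is protocol content, and that no later analysis can recover a visit 1 on-device test done without lenses. Refractive errors up to ±8.00 D sphere and −4.00 cylinder are eligible, so the missing correction need not be trivial. The refraction is done at visit 1 itself, so the need for lenses may first come to light on the day of testing. The deadline, read literally, concerns ordering the lenses before home use and not having them fitted for a test. Practice could also differ between participants. On payment, the protocol itself calls the parts visits and pays by the visit.

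Part of this stands. The sequence within a split visit 1 and the way its parts count for payment are not written down, and a colleague could fairly ask. Two things weaken it. First, the stated reason for splitting the visit is to wait for the lenses, and staff who split it for that reason would sensibly do the on-device testing once the lenses are in. Testing without them would defeat the purpose of the second attendance. Second, the correction worn off the device is a separate matter that applies to every participant, split visit or not. Best-corrected eligibility and the visit 1 refraction point to testing with the refraction found, and testing procedures commonly settle the rest. The travel-time wording concerns time and not cost, so it adds nothing to the payment point.

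**Conclusion.** No change follows. The arithmetic is right, since three trips at the stated rate exceed the cap by $25, but a stated maximum is not contradicted by a higher uncapped sum. The amount, at most $1,250 across 50 participants and possibly nothing, has no bearing on any estimate. Section 1.3 and the Brief Overview are compatible once both parts are read as visit 1.

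The possible mixing of lens correction with home use is conditional on a sequence the protocol does not prescribe. It is limited to comparisons that use the visit 1 on-device result and to participants who need lenses, of whom there could be anywhere from 0 to 50 among the minimum 50. A trial run as written can be sound. What remains is an operational detail that site staff would be expected to fill sensibly.

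This rests on two assumptions: that staff test on the device after the inserts are fitted, and that the main comparison does not depend on uncorrected on-device results from visit 1. The protocol says nothing against either.

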1.1 Screening/Recruitment Procedures

Potential participants may be identified by healthcare staff who are part of their normal clinical care or research staff. Potential participants may also hear about the study by word of mouth or by their ophthalmologist.

1.1.1 Inclusion/Exclusion Criteria

Inclusion Criteria

- Aged 18 to 90.
- Best-corrected visual acuity between 20/50 to 20/400 in the better eye.
- Subjects who have been diagnosed with an ocular condition causing visual impairment
- Have a functional binocular field of view of at least 20 degrees.
- Visual status stable for at least six months.
- Demonstrate visual benefit from magnification.
- Agree to wear the eSight Go in a variety of situations in the home and community.
- Score ≥ 20 on the Short Orientation-Memory-Concentration Test of Cognitive Impairment (OMCT).
- Subject must be able to provide an informed consent
- Subject must agree to use eSight Eyewear only under conditions that will not jeopardize the safety of either the user or the device.

Exclusion Criteria

- Participant must not be currently undergoing any medical or surgical procedures resulting in unstable vision.

- Participants who have undergone cataract, refractive, or other surgical procedures related to vision in the six-month period prior to study enrollment.
- Severe (>20/400) visual impairment in the better seeing eye.
- Cognitive limitations (< 20 on OMCT).
- Participants who have undergone any vision-related injections (e.g. anti-VEGF) in the two-month period prior to the study because of active bleeding in the retina. Ongoing anti-VEGF treatments are permitted if the participant is in a "Treat and Extend" or pro re nata ("PRN") disease management, and macula is dry.
- Participants are unable or unwilling to adhere to the examination schedules as they are described in the study protocol. This may also include participants already enrolled, who for whatever reason, have become unable or unwilling to continue the study. This may also include participants for whom the travel time to/from the study site is unacceptable.
- Participants who self-report a history of alcoholism, drug abuse, or psychosis.
- Participants who exhibit clinical evidence of depression, poor motivation, emotional or intellectual problems, or any other conditions which would likely limit validity of consent or appropriate responses to participate in the study or who are deemed unsuitable psychologically or physiologically for study participation by the investigator.
- Participants who may have a conflict of interest with eSight Corp, which could reasonably influence their participation in the study.
- Refractive error outside the range correctable by lens inserts in the device (> +/-8.00 D sph or -4.00 cyl)

1.2 Informed Consent Process

Informed consent will be obtained by approved study staff in a quiet area to allow for answering all questions.

- Participants must be able to provide consent
 - Must give accurate yes/no responses
- This study does not allow consent to be provided by a legally authorized representative (LAR)

1.3 Assessments

Participants will complete assessments four times, twice at visit 1 and twice at visit 2, except for the OMCT and the refraction which will only be performed once at visit 1.

Study Timeline

5/2025	5/2025-4/2026			5/2026-7/2026
Open enrollment	Visit 1	4 Weeks At Home Usage	Visit 2	Complete Analysis, Study Close Out

Assessments will include the following procedures:

Primary Aim Assessments (Visual)

- Early Treatment Diabetic Retinopathy Study Chart (ETDRS)
- MNREAD
- MARS Test
- NEI VFQ-25
- Reading Behavior Inventory
- Refraction Test

Secondary Aim Assessments (Mobility & Cognitive)

- Dynamic Gait Index
- Timed Up and Go
- Spatiotemporal Gait Kinematics
- OMCT
- PROMIS Short Form v2.0 - Cognitive Function 8a

Questionnaires

- Demographic information
- Ophthalmic History
- 36-Item Short Form Health Survey
- Cybersickness in Virtual Reality
- Device Usage Willingness and Participation
- Activities Balance Confidence Scale

1.4 Intervention

Participants will take the device home for 4 weeks to use in daily living, such as the home and community settings. There will be regular follow-up phone calls once per week from a member of the research team (e.g., an occupational therapist, or low vision therapist) who is familiar with the device to assist with possible troubleshooting as well as device use strategies. The follow up calls will also collect information about device use time and activities. The device will be returned at visit 2.

1.5 Data Analysis

Data will be captured during all assessments. Data will be compared against normative values, when available and change scores from pre- to post-testing will be calculated for absolute differences. Continuous data will be compared pre- to post-testing using independent samples t-tests. Ordinal data, including all questionnaires, will be evaluated using a Mann-Whitney U test.

Section 2: Risk Information

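### Section 1.5 names independent-samples tests for pre-to-post data from the same participants; if repeat scores correlate positively, p-values are too large and power is lost

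*Protocol*

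**What the plan says.** The analysis rule is in Protocol section 1.5. For continuous outcomes: "Continuous data will be compared pre- to post-testing using independent samples t-tests". For the rest: "Ordinal data, including all questionnaires, will be evaluated using a Mann-Whitney U test". The same section also says that "change scores from pre- to post-testing will be calculated for absolute differences".

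The design is in the Brief Overview and section 1.3. The Overview says "The study will comprise at least 50 vision impaired individuals" and "Participants will receive a personal eSight device and comprehensive training on its operation at visit 1". Section 1.3 says "Participants will complete assessments four times, twice at visit 1 and twice at visit 2", with the cognitive screen and the refraction as the only exceptions. No control arm or other comparison group is described, and no paired test or repeated-measures model is named.

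**The concern.** The independent-samples t-test and the Mann-Whitney U test are built for two sets of unrelated people. Here the pre and post scores come from the same people, whichever of the four assessments are taken as pre and post. Section 1.5 recognises the pairing when it calculates change scores, then names tests that discard it.

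The two sentences govern every pre-to-post test the protocol names, for the primary aim (acuity, reading, quality of life) and the secondary aim (mobility, balance, cybersickness). If a person's scores correlate positively over time, the planned tests overstate the uncertainty of the mean change. A real but modest improvement is then more likely to be missed. So is a real but modest worsening in a safety-relevant measure such as Timed Up and Go or gait, in a study whose section 2.1 lists dizziness and falls among the risks.

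The mean change itself, the change scores and the comparison with normative values are not affected.

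**Working it through.** **Inputs from the protocol.** One cohort, n = 50 (the stated minimum), the same people at each assessment, and the tests named in section 1.5. The protocol gives no alpha, power, SD, effect size or correlation with the sample size, so there is no figure of its own to reproduce.

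**Assumptions.** Two-sided 5%; 50 complete pairs; equal SDs pre and post; r from 0.3 to 0.8, with r = 0 as a reference; true shifts expressed in SDs of a single measurement.

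**Step 1: standard error.** For paired data the variance of the mean change is 2·SD²·(1−r)/n. The independent-samples test uses 2·SD²/n. The ratio of standard errors is 1/sqrt(1−r): 1.20, 1.41, 1.83 and 2.24 at r = 0.3, 0.5, 0.7 and 0.8. The protocol plans no confidence interval, but one built from the unpaired standard error would be too wide by the same factor.

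**Step 2: actual type I error of the planned t-test.** Large-sample formula: 2·(1 − Φ(1.96/sqrt(1−r))). At r = 0.5 this is 2·(1 − Φ(2.77)) = 0.56%. Simulation with n = 50 (200,000 bivariate-normal datasets per setting) gives 2.0%, 0.6%, 0.06% and below 0.01% at r = 0.3, 0.5, 0.7 and 0.8. The paired test stays at about 5% throughout.

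**Step 3: power, planned / paired t-test (%), from the same simulations.**

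| True shift | r = 0.3 | r = 0.5 | r = 0.7 | r = 0.8 |
|---|---|---|---|---|
| 0.3 SD | 29 / 42 | 25 / 55 | 20 / 77 | 16 / 91 |
| 0.4 SD | 51 / 65 | 51 / 79 | 52 / 95 | 52 / 99 |
| 0.5 SD | 73 / 83 | 77 / 93 | 82 / 99 | 86 / >99 |
| 0.6 SD | 89 / 94 | 92 / 99 | 96 / >99 | 98 / >99 |

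The paired column agrees with the noncentral t distribution (at r = 0.5: 54.8, 79.2, 93.4 and 98.6%). At r = 0 nothing is lost (32 / 31% at 0.3 SD; 70 / 69% at 0.5 SD). In this table the loss exceeds half of the paired power only at 0.3 SD with r of 0.5 or more. It is 12–18% of paired power at 0.5 SD and 2–7% at 0.6 SD.

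**Step 4: smallest observed mean change that reaches p < 0.05, in either direction.**
- Planned: t(0.975, 98 df)·sqrt(2/50) = 1.984 × 0.200 = 0.397 SD, whatever r is.
- Paired: t(0.975, 49 df)·sqrt(2(1−r)/50) = 2.010·sqrt(2(1−r)/50), which is 0.336, 0.284, 0.220 and 0.180 SD at r = 0.3, 0.5, 0.7 and 0.8.

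**Step 5: ordinal outcomes.** A 7-level score was simulated by cutting a latent normal at ±0.3, ±0.9 and ±1.5, with r and the shift on the latent scale (40,000 datasets per setting). At r = 0.3, 0.5, 0.7 and 0.8:
- Mann-Whitney type I error is 2.2%, 0.8%, 0.09% and below 0.01%.
- Mann-Whitney / signed-rank power at 0.3 SD is 26/39, 24/50, 19/70 and 16/84%.
- At 0.5 SD it is 68/80, 71/90, 75/98 and 79/>99%.
- At r = 0 the two tests are equal (30% at 0.3 SD, 66% at 0.5 SD).

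**The case against.** Nobody can defend the choice of tests, but four points limit how much it matters.

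- **Conservative is not the same as uncontrolled.** With positive r, false positives stay at or below 2.0% over the assumed range, so a significant result can still be believed. This stands. The p-values are wrong, but on the cautious side. The direction reverses only if r is negative: at r = −0.3 the planned t-test's actual type I error is about 8.6%. Section 1.1.1 requires vision stable for at least six months, and participants are retested after four weeks, so a positive r is the reasonable expectation.
- **Large effects survive.** At a shift of 0.8 SD, planned and paired power are about 99.1 and 99.7% at r = 0.3, and closer still at higher r. Eligibility requires a demonstrated benefit from magnification, so large with-device shifts in acuity or reading are plausible. This also stands. The loss falls mainly on outcomes with small shifts, perhaps quality of life, gait or the assessment without the device.
- **Equal SDs are not assured**, because pre and post may be measured without and with the device. If one SD were twice the other, the factor would be sqrt(5/(5−4r)): 1.29 instead of 1.41 at r = 0.5, and 1.67 instead of 2.24 at r = 0.8. The direction is unchanged and the loss smaller.
- **The analysis can be corrected later without new data.** That is true, but changing the test after results are seen would look data-driven.

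A statistical analysis plan, if there is one, does not remove the point. The protocol states a method rather than leaving it open, so a correct plan would contradict it.

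**Conclusion.** The concern holds: the tests in section 1.5 are wrong as written for a single cohort measured repeatedly. That conclusion needs no assumption. Its size does: it rests on 50 complete pairs, equal SDs, a two-sided 5% level and r between 0.3 and 0.8. On those terms the consequence ranges from severe at a 0.3 SD shift with high correlation to negligible at 0.8 SD. The planned t-test cannot declare an observed change below about 0.40 SD significant, where a paired test could do so at 0.18 to 0.34 SD. The risk is missed benefit and missed harm, not false claims of benefit. It should be corrected before analysis because it touches every pre-to-post test and is almost free to correct.

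**What to change.** Replace the two test sentences in section 1.5:

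- **Continuous outcomes:** paired t-test on within-person differences, or a linear mixed model with a participant random effect when more than two of the four assessments are used.
- **Ordinal outcomes and repeated questionnaires:** Wilcoxon signed-rank test. Forms with no pre-post change to test, such as demographics and ophthalmic history, fall outside this.
- **Reporting:** within-person change with a 95% confidence interval.

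A paired test needs a named pair, so the new wording should also say which of the four assessments are pre and post. Section 1.5 does not say so now; that is a separate gap.

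The cost is two sentences of protocol wording. No new data and no extra participants are needed.
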